**RUTGERS | eIRB**  
**APPROVED**

tumor-immune system interaction in the tumor microenvironment as a target for therapeutic manipulation in combination strategies.

#### **1.4.8 Clinical Safety Summary**

Nivolumab and pembrolizumab have been administered to tens of thousands of patients, and are generally well-tolerated, but serious side effects related to auto-immunity can occur. The most common adverse reactions are fatigue, rash, musculoskeletal pain, pruritus, diarrhea, nausea, asthenia, cough, dyspnea, constipation, decreased appetite, back pain, arthralgia, upper respiratory tract infection, pyrexia, vitiligo, and headache. The most common laboratory abnormalities are hyponatremia and liver function test abnormalities.

Refer to the United States Prescribing Information (USPI) for a full description of the clinical safety of each agent.

#### **1.4.9 Supporting Data for Combination Study**

##### **Riluzole for cancer therapy**

Riluzole decreases migration, invasion and proliferation of melanoma cells in xenograft models. Based on this finding, we evaluated riluzole, for potential anti-cancer activity in a preclinical setting and in a Phase 0 clinical trial for advanced stage melanoma. We tested the efficacy of riluzole in melanoma patients with a poor prognosis and severely limited treatment options. Twelve subjects with Stage III/IV melanoma were treated with riluzole for two weeks. Four subjects demonstrated reduction MAPK or PI3K/AKT signaling pathway and involution of tumors. Two other subjects demonstrated a clinical response as on radiologic examination. Objective response was observed in 34% in patients after only 14 days of treatment (riluzole 100 mg every 12 hours).

##### **GRM1 signal transduction up-regulates factors that suppress tumor immunity**

Further studies on the downstream effects of GRM1 signal transduction suggest that another effect of GRM1 signal transduction is suppression of tumor in the microenvironment. In order to study downstream signaling along the GRM1 pathway we designed a set of cell lines where the parental lines had low or absent GRM1 expression and the modified lines had enhanced expression of this cell surface receptor. We previously reported that enhanced GRM1 expression resulted in enhanced tumor angiogenesis and in vivo tumor growth. Using the same cell lines we have now demonstrated that xenografts produced from melanoma cell lines with enhanced GRM1 expression have a more pro-tumor microenvironment as compared to xenografts

Protocol Number: RCINJ# 051707

PI Name: [name]

Protocol Title: A Phase I Study to Evaluate the Safety of Trigriluzole (FC-4157/BHV-4157) in Combination with PD-1 Blocking Antibodies

19

RESERVED FOR IRB STAMP  
DO NOT MODIFY THIS SPACE

 **RUTGERS | eIRB**  
APPROVED  
Form Version v120116

IRB ID: Pro20170000453  
Approval Date: 10/4/2019  
Expiration Date: 4/3/2020

produced from parental lines. Enhanced GRM1 expression results in up-regulated expression of CCL2 and M-CSF in these melanoma lines. Over-expression of M-CSF and its receptor, CSF-1R, in tumors has been associated with a poor prognosis and M-CSF and CCL4 have also been implicated in mobilization of tumor-associated macrophages into the tumor microenvironment.

**Xenografts produced from melanoma cell lines with enhanced GRM1 expression have a more pro-tumor microenvironment as compared to xenografts produced from parental lines**

[figure not shown]
To see if our *in vitro* findings of up-regulated expression of CCL2 and M-CSF with enhanced GRM1 expression would translate to a more tumor-permissive microenvironment *in vivo*, we produced xenografts with the parental and enhanced GRM1 expressing cell lines. We found an increased number of macrophages in the spleens and peripheral blood in the xenografts produced from the enhanced GRM1 expressing cell lines as compared to the parental lines. The GRM1 enhanced tumors also showed greater amounts of angiogenesis and an overall decrease in infiltrating lymphocytes as compared to the parental tumors.

**Eliminating macrophages inhibits tumor growth in a GRM1 driven transgenic mouse melanoma model**

To further test our hypothesis that GRM1 signal transduction results in suppression of tumor immunity through an increase in M2 suppressive macrophages secondary to up-regulation of M-CSF, we treated a small group of melanoma-prone transgenic mice with liposome-encapsulated clodronate. The transgenic line ectopically expresses GRM1 and this drives the development of melanocytic lesions, indistinguishable from melanoma, with a 100% penetrance. Liposome-encapsulated clodronate is a macrophage “suicide” approach, which is used to deplete macrophages *in vivo*. The liposome-encapsulated clodronate can be taken up by phagocytic cells but not excreted. This results in the death of these cells. We treated a cohort of these animals with Liposome-encapsulated clodronate, and confirmed that we were suppressing macrophages in these animals. An untreated cohort was used as controls. We found that both treated and untreated animals developed pigmented lesions early on, but in the treated group these lesions did not continue to grow and the animals remained healthy for up to 19 months. The untreated controls had to be sacrificed at 3 months because of overgrowth of tumor (Figure 1).

**Figure 1. Eliminating macrophages inhibits tumor growth in a GRM1 driven transgenic mouse melanoma model**

**Figure 1 left:** Melanoma-prone transgenic mice were either not treated (top panel, at 3 months old) or treated with liposome-encapsulated clodronate for 7 months (bottom panel, at 9 months old). Right: Flow cytometry analysis with CD11b, a pan macrophage marker showed 90% reduction in clodronate-treated spleen.

A subset of the treated animals was taken off of liposome-encapsulated clodronate and within 2 weeks they once again began to show rapid tumor growth and had to be sacrificed one month later. Necropsy demonstrated a resurgence of macrophages populations within this subset of animals. This demonstrates that in a transgenic model of melanoma driven by GRM1 expression, depletion of macrophages will suppress tumor growth and reconstitution of macrophages results in a rapid return of tumor growth.

#### 1.4.10 Summary of Supportive Data

This body of work demonstrates that GRM1 signal transduction appears to suppress tumor immunity, likely through the up-regulation of tumor associated M2 macrophages. Blocking the pathway with riluzole or trigriluzole could reduce or reverse this immunosuppressive tumor microenvironment in patients with cancer and increase TILs. It would therefore be logical to combine an agent such as trigriluzole, with an immune-based therapy such as an immune checkpoint inhibitor, in patients with advanced cancer. This forms the rationale for the phase I trial that we propose in this application.

While many combinations with a PD-1 blockade backbone are under investigation, there is the potential for toxicity with overlapping side effects. Dual checkpoint blockade with nivolumab in combination with ipilimumab, is effective in treating patients with metastatic melanoma and potentially other cancers. Treatment results in a response rate of 55%, but due to overlapping toxicity of these two, grade 3-4 immune-related adverse

events occur in 55% of subjects. Because riluzole and trigriluzole have few adverse events and the toxicity does not overlap with the toxicity of the checkpoint inhibitors, we hope that the combination of PD-1 blockade and trigriluzole in this clinical study will be tolerable and effective.

### **1.5 Sample Size Justification**

Four dosing cohorts are planned in order to test a dose of trigriluzole up to 280 mg PO BID. We do not anticipate testing higher doses. With approximately 3 subjects per dosing cohort, the required sample size is 9 - 21 subjects for testing trigriluzole with nivolumab. The MTD will then be tested with pembrolizumab and an additional 3-6 subjects will be required. The total sample size will be 12 - 27 subjects (9 – 21 in the nivolumab group, plus 3 – 6 in the pembrolizumab group).

### **1.6 Study Variables**

- **Independent Variables, Interventions, or Predictor Variables**
  - Treatment variable: Dose of trigriluzole
  - Treatment variable: pembrolizumab or nivolumab
- **Dependent Variables or Outcome Measures**
  - Adverse events
  - Tumor response
  - Survival time

### **1.7 Drugs/Devices/Biologics**

#### **1.7.1 Drug/Device Accountability And Storage Location**

Investigational drug will be stored in the RCINJ Research Pharmacy, a shared resourced. The investigational pharmacists will be responsible for preparation, dispensing, disposal, and drug accountability.

### **1.7.2 Drug Accountability**

The investigator is required to maintain adequate records of receipt, dispensing and final disposition of study drug. This responsibility has been delegated to the pharmacy. Include on receipt record (e.g. packing slip) from and to whom study drug was shipped, date, quantity, and batch or lot number. On dispensing record, note quantities and dates study drug was dispensed to and returned by each subject. It is permitted to dispense supply that will last until the next scheduled visit plus 1-3 days “emergency” supply to ensure patient has access to drug in the event that the visit is unexpectedly delayed.

### **1.7.3 Drug Destruction/Disposal**

Empty and partially empty containers of study drug will be disposed of in accordance with institutional policies and procedures. Unused containers of study drug will be returned to the study sponsor following completion of the study.

### **1.7.4 Pharmaceutical Information**

#### **Investigational Agent: Trigriluzole (BHV-4157/FC-4157)**

The investigational drug will be supplied by Biohaven Pharmaceuticals. Refer to the Investigational Drug Brochure (IDB)

- Product description: The dosage form for the intended clinical trials is Capsules for oral administration, consisting of a common blend formulation of the drug substance with standard excipients filled in size 1 hard gelatin capsule shells at a strength of 140 mg. The manufacturing and packaging of BHV-4157 capsules in bottles (35-count, 75 cc) is by QS Pharma, and the labeling of clinical supplies is by The Coghlan Group.
  - Appearance: Size 1 White Opaque Capsules filled with white to off-white powder.
  - Storage and Handling: Controlled Room Temperature (68° - 77°F or 20° - 25°C).
  - Stability: The common blend capsules are expected to be stable for at least 1 year. Stability studies are ongoing and are expected to extend the retest period of clinical supplies.
- Preparation (how the dose is to be prepared): n/a
- Route of administration: oral
  - Drug Interactions: Clinical drug interaction studies for trigriluzole have not been conducted yet. Trigriluzole, itself, is not expected to interfere with drug metabolism and its cleavage via plasma peptides render it unlikely to be affected significantly by liver cytochrome P450 inhibitors.

**Commercial Agent: Pembrolizumab (KEYTRUDA)**

Refer to the package insert for agent information.

[http://www.merck.com/product/usa/pi\\_circulars/k/keytruda/keytruda\\_pi.pdf](http://www.merck.com/product/usa/pi_circulars/k/keytruda/keytruda_pi.pdf)

Reconstitution of KEYTRUDA for Injection (Lyophilized Powder)

- Add 2.3 mL of Sterile Water for Injection, USP by injecting the water along the walls of the vial and not directly on the lyophilized powder (resulting concentration 25 mg/mL).
- Slowly swirl the vial. Allow up to 5 minutes for the bubbles to clear. Do not shake the vial.

Preparation for Intravenous Infusion

- Visually inspect the solution for particulate matter and discoloration prior to administration. The solution is clear to slightly opalescent, colorless to slightly yellow. Discard the vial if visible particles are observed.
- Dilute KEYTRUDA injection (solution) or reconstituted lyophilized powder prior to intravenous administration.
- Withdraw the required volume from the vial(s) of KEYTRUDA and transfer into an intravenous (IV) bag containing 0.9% Sodium Chloride Injection, USP or 5% Dextrose Injection, USP. Mix diluted solution by gentle inversion. The final concentration of the diluted solution should be between 1 mg/mL to 10 mg/mL.
- Discard any unused portion left in the vial.

Storage of Reconstituted and Diluted Solutions

The product does not contain a preservative. Store the reconstituted and diluted solution from the KEYTRUDA 50 mg vial either:

- At room temperature for no more than 6 hours from the time of reconstitution. This includes room temperature storage of reconstituted vials, storage of the infusion solution in the IV bag, and the duration of infusion.
- Under refrigeration at 2°C to 8°C (36°F to 46°F) for no more than 24 hours from the time of reconstitution. If refrigerated, allow the diluted solution to come to room temperature prior to administration. Store the diluted solution from the KEYTRUDA 100 mg/4 mL vial either:

- At room temperature for no more than 6 hours from the time of dilution. This includes room temperature storage of the infusion solution in the IV bag, and the duration of infusion.
- Under refrigeration at 2°C to 8°C (36°F to 46°F) for no more than 24 hours from the time of dilution. If refrigerated, allow the diluted solution to come to room temperature prior to administration. Do not freeze.

#### Administration

- Administer infusion solution intravenously over 30 minutes through an intravenous line containing a sterile, non-pyrogenic, low-protein binding 0.2 micron to 5 micron in-line or add-on filter.
- Do not co-administer other drugs through the same infusion line.

#### **Commercial Agent: Nivolumab (OPDIVO)**

Refer to the package insert for agent information.

[http://packageinserts.bms.com/pi/pi\\_opdivo.pdf](http://packageinserts.bms.com/pi/pi_opdivo.pdf)

#### Preparation and Administration

Visually inspect drug product solution for particulate matter and discoloration prior to administration. OPDIVO is a clear to opalescent, colorless to pale-yellow solution. Discard the vial if the solution is cloudy, discolored, or contains extraneous particulate matter other than a few translucent-to-white, proteinaceous particles. Do not shake the vial.

- Withdraw the required volume of OPDIVO and transfer into an intravenous container.
- Dilute OPDIVO with either 0.9% Sodium Chloride Injection, USP or 5% Dextrose Injection, USP to prepare an infusion with a final concentration ranging from 1 mg/mL to 10 mg/mL.
- Mix diluted solution by gentle inversion. Do not shake
- Discard partially used vials or empty vials of OPDIVO.

#### Storage of Infusion

The product does not contain a preservative. After preparation, store the OPDIVO infusion either:

Protocol Number: RCINJ# 051707

PI Name: [name]

Protocol Title: A Phase I Study to Evaluate the Safety of Trigriluzole (FC-4157/BHV-4157) in Combination with PD-1 Blocking Antibodies

25

RESERVED FOR IRB STAMP  
DO NOT MODIFY THIS SPACE

Form Version v120116

**RUTGERS | eIRB**  
**APPROVED**

IRB ID: Pro20170000453  
Approval Date: 10/4/2019  
Expiration Date: 4/3/2020

- at room temperature for no more than 4 hours from the time of preparation. This includes room temperature storage of the infusion in the IV container and time for administration of the infusion or
- under refrigeration at 2°C to 8°C (36°F to 46°F) for no more than 24 hours from the time of infusion preparation. Do not freeze.

#### Administration

- Administer the infusion over 60 minutes through an intravenous line containing a sterile, non-pyrogenic, low protein binding in-line filter (pore size of 0.2 micrometer to 1.2 micrometer).
- Do not co-administer other drugs through the same intravenous line. Flush the intravenous line at end of infusion.

### **1.7.5 TREATMENT PLAN**

#### **1.7.5.1 Study Agents**

##### **Trigriluzole**

All patients will receive trigriluzole, which will be self-administered as continuous oral daily to BID dosing, depending on the dosing cohort (see Table 3). Subjects will begin therapy with the prescribed dose of trigriluzole for a run-in period of 14 days. After the lead-in period, subjects will continue trigriluzole and begin therapy with pembrolizumab or nivolumab. The first dose of trigriluzole will be administered in the clinic. The patient will have PK and EKG done after the first dose.

##### **Anti-PD-1 antibody (pembrolizumab or nivolumab)**

PD-1 inhibitor treatment will consist of either nivolumab or pembrolizumab. PD-1 inhibitor will begin at Week 1 (following 14 day lead-in with trigriluzole). Subsequent PD-1 inhibitor treatments will occur at 2-3-week intervals, depending on the schedule of the PD-1 inhibitor as per the Study Calendar.

##### **Treatment Assignment**

Dose escalation of trigriluzole with nivolumab will proceed up to a maximum of 280 mg PO BID to identify the MTD. Subjects will be enrolled on the trial starting with Cohort 1 (Table 3) in a starting cohort size of 3 subjects. Subjects will be followed for 4 weeks to observe for dose-limiting toxicity (DLT). The decision to escalate or deescalate to a new dosing cohort or

to expand a dosing cohort will be made using the procedure described in the statistical analysis section.

**Table 3. Dosing cohorts for Trigriluzole + Nivolumab**

Escalation cohort	Nivolumab	Trigriluzole
Cohort -1	240mg IV Q 2 weeks	140 mg PO every other day (QOD)
Cohort 1	240mg IV Q 2 weeks	140 mg PO daily
Cohort 2	240mg IV Q 2 weeks	140 mg PO BID
Cohort 3	240mg IV Q 2 weeks	140 mg PO QAM+ 280 mg PO QHS
Cohort 4	240mg IV Q 2 weeks	280 mg PO BID

After the MTD of trigriluzole with nivolumab is identified, the MTD of trigriluzole will be tested in combination with pembrolizumab in 3-6 patients in Cohort P1. If the MTD is not tolerable in Cohort P1, the dose will be decreased by 1 level.

**Table 4. Dosing cohort for Trigriluzole + Pembrolizumab**

Escalation cohort	Pembrolizumab	Trigriluzole
Cohort P -1	200 mg IV Q3 weeks	MTD -1 level
Cohort P1	200mg IV Q3 weeks	MTD

### **1.7.6 Treatment Administration**

#### **Trigriluzole Administration**

Trigriluzole will be self-administered by the patient. Trigriluzole will be first administered in the clinic setting. Trigriluzole can be taken without regards to meals (on a full stomach or an empty stomach). Morning or evening administration is acceptable for once daily dosing. No weight-based dosing calculation is necessary as trigriluzole is administered using flat dosing.

**Lead-in period.** Subjects will begin therapy with continuous oral dosing of trigriluzole for a lead-in period of 14 days (Week -2, Day -14 to Week -1, Day -1). Day -1 is followed by Day 1 (There is no Day 0 or Week 0).

**Combination treatment.** At the start of Week 1, subjects will continue oral dosing of trigriluzole and begin therapy with PD-1 inhibitor. On the days of IV treatment visits, there is no window for administration of trigriluzole with respect to the PD-1 inhibitor.

**Compliance/adherence assessment.** Subjects will be *strongly encouraged* to use the Pill Diaries that are provided by the study. If a patient reports compliance <80% of days, they should be re-educated by the research nurse and/or treating investigator on instructions for dosing trigriluzole at home.

#### **Nivolumab or Pembrolizumab Administration**

Nivolumab or pembrolizumab will be administered in the outpatient setting.

Nivolumab will be administered at the FDA-approved dose and schedule of 240 mg IV Q2 weeks over 60 minutes.

Pembrolizumab will be administered at the FDA-approved dose and schedule of 200 mg IV Q3 weeks over 30 minutes.

### **1.7.7 Dose Modifications and Withholding**

As toxicity of these agents is largely non-overlapping, management of toxicity is dependent on which agent is more likely to have resulted in the toxicity. Vertigo, somnolence, and circumoral paresthesia should be attributed to trigriluzole. Immune-related adverse events should be attributed to the anti- PD-1 antibody. Refer to agent-specific management instructions below for dose modifications and holdings.

*Overlapping toxicities of trigriluzole and anti- PD-1 antibody include fatigue, asthenia, nausea, dizziness, diarrhea, anorexia and liver injury. When these toxicities occur, both drugs should be held until toxicity resolves to grade 0-1.*

Study therapy (both agents) may be held for up to 6 consecutive weeks. Subjects who are not able to resume at least 1 study drug within a period of 6 weeks should be removed from the active treatment phase of the study and begin follow-up procedures.

Dosing interruptions are permitted in the case of medical / surgical events or logistical reasons not related to study therapy (e.g., elective surgery, unrelated medical events, patient vacation, and/or holidays). Missed doses should be omitted, not delayed. Subjects should be placed back on study therapy within 3 weeks of the scheduled interruption, unless otherwise discussed with the study PI or co-PI. The reason for interruption should be documented in the patient's study record. Tumor assessments should continue per the study calendar even if study medication was missed.

Delays due to holidays, weekends and bad weather will be permitted and will not be counted as a protocol violation, and efforts will be made to get the patient back on the original schedule so that assessments are uniform across subjects. If correlative samples are collected and the scheduled treatment that day is delayed/held for any reason, there is no need to re-collect correlative samples.

### **Trigriluzole**

**Grade 3-4 Toxicity.** Any Grade 3 or 4 adverse event thought to be related (possibly, probably, or definitely) to trigriluzole will require the dose to be held until the event recovers to Grade 1 or less. When therapy resumes, the dose must be reduced by one level. If the adverse event does not improve to Grade 0-1 within 4 weeks of holding trigriluzole, the patient will be removed from the study.

**Grade 1-2 Toxicity.** Grade 1-2 adverse events do not require dose adjustment, except if the patient/physician considers them to be serious or intolerable—in this case, the dose may be reduced by one level as per the table below at the discretion of the treating investigator. An example is grade 1 dizziness that the patient finds intolerable.

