### **1.3.5 Active phase, combination treatment**

After Week 2, regular study visits will occur in the outpatient clinic at an interval of 14 or 21 days (depending on whether treatment includes nivolumab or pembrolizumab) as per the Study Calendar.

Subjects will receive treatment up to 109 weeks. Subjects may elect to discontinue therapy at any time for any reason. Subjects will remain on the active treatment phase of the study until confirmed disease progression, unacceptable toxicity, or withdrawal of consent, up to a maximum treatment duration of 109 weeks. Once the subject discontinues active treatment, the subject will enter the follow-up phase.

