### **1.3.6 Off treatment procedures (up to 1 year)**

If a subject has discontinued active treatment due to reasons other than PD, the subject will continue to have toxicity assessments (H&P and bloodwork) and tumor assessments (CT scans, etc.) Q12 weeks (window can be widened to  $\pm$  28 days) for up to 1 year from the start of treatment.

Subjects should be strongly encouraged to adhere to in-person toxicity assessments and tumor assessments per protocol for the 1-year active phase of the protocol. However, subjects who are unable or unwilling adhere to in-person assessments (but do not withdraw consent to be followed) should be contacted Q12 weeks to assess for adverse events. Safety labs and tumor assessments should be obtained at outside facilities if possible. This practice is allowable because it is preferable over removal of the patient from study entirely, and it will not be considered to be a protocol deviation.

If cancer return/progression is observed within the 1-year treatment period (in the opinion of the treating investigator, no strict criteria) and the risk/benefit ratio of restarting study therapy (combination therapy or trigriluzole monotherapy) is acceptable to the treating investigator, the patient may be restarted on therapy with the approval of the PI for up to 12 additional months.

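### Section 1.7.7 gives conflicting instructions for trigriluzole-related Grade 3-4 events unresolved after a 4-week hold, and removal from the study conflicts with the protocol's own follow-up provisions

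*Combined protocol and SAP*

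**What the plan says.** Two rules in section 1.7.7 bear on a long hold.

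- **Opening of 1.7.7 (general).** "Study therapy (both agents) may be held for up to 6 consecutive weeks". The test at the limit concerns either drug: "Subjects who are not able to resume at least 1 study drug within a period of 6 weeks" are the ones who leave, and they "should be removed from the active treatment phase of the study and begin follow-up procedures". The same text points forward: "Refer to agent-specific management instructions below for dose modifications and holdings". For listed overlapping toxicities, which include liver injury, it adds: "When these toxicities occur, both drugs should be held until toxicity resolves to grade 0-1".
- **Trigriluzole, Grade 3-4 Toxicity (agent-specific).** This covers Grade 3 or 4 events judged at least possibly related to trigriluzole. The limit is 4 weeks: "If the adverse event does not improve to Grade 0-1 within 4 weeks of holding trigriluzole, the patient will be removed from the study". It mentions neither follow-up nor the antibody.

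Four places deal with subjects who stop treatment.

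- **Section 1.3.5.** "Once the subject discontinues active treatment, the subject will enter the follow-up phase".
- **Section 1.3.6.** "If a subject has discontinued active treatment due to reasons other than PD, the subject will continue to have toxicity assessments", together with tumor assessments, every 12 weeks until one year after treatment began.
- **Timing of Assessments (1.7.12).** CT scans go on to Week 49 after a stop for any reason except PD.
- **Follow-up calendar (1.10), footnote 1.** It keeps the same group in scans and visits to Week 49, and gives toxicity as an example of such a reason.

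**The concern.** A subject whose trigriluzole-related Grade 3-4 event has not recovered at 4 weeks can meet two rules with different outcomes. Under one, the subject may still be held, may go on with one drug, or leaves treatment and is followed. Under the other, the subject leaves the study. Site staff cannot comply with both.

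The statistical stake is in the disposition. Removal would be triggered by an outcome of interest, namely trigriluzole toxicity that does not resolve. If it ended observation, the missing data would not be missing at random with respect to safety. The subjects dropped would be those whose later course says most about how the combination is tolerated, and their later response, PFS and survival would be lost with it.

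**Working it through.** No power, alpha or sample-size figure in the plan depends on this point, so there is nothing to reproduce. The check sets the texts side by side and then gives simple arithmetic for scale.

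**1. Where the two rules in 1.7.7 meet**

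| Situation | Opening of 1.7.7 | Trigriluzole, Grade 3-4 |
|---|---|---|
| (a) Both drugs held, event unresolved, weeks 4 to 6 | Hold may continue to week 6 | Removed from the study at week 4 |
| (b) Trigriluzole held beyond 4 weeks, antibody continues or could resume | Subject stays, since one drug is enough | Removed from the study at week 4 |
| Unresolved at the limit, neither drug resumable | Leaves active treatment, enters follow-up | Removed from the study, follow-up not mentioned |

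The length of conflict in (a) is 6 − 4 = 2 weeks. In (b) it has no fixed length, because the 6-week limit concerns holding both agents. Situation (a) is foreseeable: section 1.4.2 describes transaminase elevation as riluzole's dose-related laboratory effect, and the PD-1 dose-modification text also requires trigriluzole to be held for liver toxicity. Situation (b) is foreseen too: Table 5 ends in discontinuing trigriluzole, and the ECG footnotes to the study calendars provide for subjects who have stopped it.

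**2. Does removal from the study mean the end of follow-up?**

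- *Suggesting that it does:* section 1.3.6 accepts remote contact because complete removal from the study would be worse. Compliance/Adherence (6.1) speaks of removal from the study for non-compliance and says those who leave for that reason are not followed. The follow-up calendar has columns for subjects off treatment but still on study, so the protocol does separate the two.
- *Suggesting that it does not:* sections 1.3.5 and 1.3.6, Timing of Assessments and the follow-up calendar all keep these subjects under observation. Section 1.7.13 has an off-study heading but lists reasons for ending treatment. Under its item (d), life-threatening drug-related toxicity ends further treatment only.

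The texts do not settle it. Read literally, a persistent Grade 3 event would end study participation, while a life-threatening one would end only treatment.

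**3. Scale, if applied literally**

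Planned total: 12 to 27 subjects (sections 1.5 and 4.1.4). Share per subject lost: 1/12 = 8.3%; 1/27 = 3.7%.

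The documents give no rate q of such events. With assumed rates, the chance of at least one is 1 − (1 − q)^N and the expected number is Nq:

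| Assumed q | N = 12: chance (expected) | N = 27: chance (expected) |
|---|---|---|
| 2% | 0.215 (0.24) | 0.420 (0.54) |
| 5% | 0.460 (0.60) | 0.750 (1.35) |
| 10% | 0.718 (1.20) | 0.942 (2.70) |

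Adverse events are collected to 30 days after the last dose (1.7.11). If both drugs stop together and are not resumed, a 28-day hold leaves 30 − 28 = 2 days. Observing late resolution then depends on the follow-up visits that a literal removal would cut off.

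**4. Effect on the MTD**

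A related Grade 3 or higher event in the DLT window is a DLT when it occurs, apart from the exception for asymptomatic amylase or lipase elevation. Later removal does not undo it. Counting Day -14 as study day 1, a hold starting on day d reaches 4 weeks at d + 28. This falls within the 5-week window (35 days) only for d ≤ 7, and never within the 4 weeks named in the DLT definition (28 days). In that narrow case, removal before day 35 could raise a question under the replacement rule (Missing data, 6.1).

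**The case against.** The strongest reply is that this is a general rule with a specific exception. The opening of 1.7.7 refers readers to agent-specific instructions, and a shorter limit for related Grade 3-4 trigriluzole events can sit under a 6-week ceiling. That has force and narrows the point. It does not say what happens to the antibody, nor why the specific rule changes the destination from follow-up to leaving the study.

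The second reply is that no data need be lost, because four other places keep these subjects in follow-up and 1.7.13 shows loose use of the phrase. This stands to the extent that loss cannot be asserted as a fact of the plan.

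A reader might infer three stronger things, none supported by the documents:

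- *That every persisting event has a 2-week conflict.* The trigriluzole rule does not reach Grade 2 overlapping toxicities or events related only to the antibody.
- *That the plan loses outcome data on these subjects.* It does so only if the removal wording is applied literally, against the follow-up provisions.
- *That each removal costs a third of a dose level.* This is true only of a cohort of exactly three. The escalation procedure allows six at a dose (one sixth), and the secondary endpoints are descriptive with no survival analysis by dose level specified.

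**Conclusion.** The point holds in a limited form. For trigriluzole-related Grade 3-4 events not back to Grade 0-1 after 4 weeks of holding, section 1.7.7 gives incompatible instructions in situations (a) and (b). Its removal wording also conflicts with sections 1.3.5 and 1.3.6, Timing of Assessments and the follow-up calendar.

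The data consequence is conditional. Under literal application, later response, PFS, survival and event-resolution data would be lost selectively for subjects with persistent trigriluzole toxicity, at 3.7% to 8.3% of the trial per subject. How many would be affected is unknown; the 2% to 10% range is an assumption made for scale. The primary endpoint is barely touched. This is an inconsistency that should be corrected, not a flaw in the dose-finding method.

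**What to change.** 1. Reconcile the opening of 1.7.7 with its Trigriluzole, Grade 3-4 text: one statement of which hold limit applies to which events, what happens when it is reached, and whether the antibody may continue. Which limit and which disposition are right is a clinical decision for the investigators, and none is proposed here.
2. State that, whichever rule is kept, a subject who leaves treatment under the trigriluzole rule is not removed from study follow-up, but continues with the assessments in sections 1.3.6 and 1.3.7 unless consent is withdrawn.

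The cost is amendment wording. The visits, scans and survival contacts already exist in those sections and in the follow-up calendar, so no new procedure is needed.
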